**Table 6-3 Criteria for interruption and re-initiation of INC280 treatment**

To be considered recommended dose modifications, unless otherwise specified as mandatory in this [Table 6-3](#). Refer to [Table 6-4](#) for follow-up evaluations as applicable.

Refer to [Table 6-4](#) for follow-up evaluations as applicable.

Recommended dose modifications for INC280	
Worst toxicity CTCAE Grade a	During a cycle of therapy
No toxicity	Maintain dose level
HEMATOLOGICAL	
Neutrophil count decreased (ANC) Neutropenia	
Grade 1 (ANC < LLN - 1500/mm  ; < LLN - 1.5 x 10  /L)	Maintain dose level
Grade 2 (ANC < 1500 - 1000/mm  ; < 1.5 - 1.0 x 10  /L)	Maintain dose level
Grade 3 (ANC < 1000 - 500/mm  ; < 1.0 - 0.5 x 10  /L)	Omit dose until resolved to ≤ grade 2, then: If resolved in ≤ 7 days, resume treatment at the same dose level If resolved in > 7 days, then ↓ 1 dose level
Grade 4 (ANC < 500/mm  ; < 0.5 x 10  /L)	Omit dose until resolved to ≤ grade 2 and then ↓ 1 dose level
Platelet count decreased (Thrombocytopenia)	
Grade 1 (PLT < LLN - 75,000/mm  ; < LLN - 75 x 10  /L)	Maintain dose level
Grade 2 (PLT < 75,000 - 50,000/mm  ; < 75 - 50 x 10  /L)	Maintain dose level
Grade 3 (PLT < 50,000 - 25,000/mm  ; < 50 - 25 x 10  /L)	Omit dose until resolved to ≤ grade 2, then: If resolved in ≤ 7 days, then maintain dose level If resolved in > 7 days, then ↓ 1 dose level
Grade 4 (PLT < 25,000/mm  ; < 25 x 10  /L)	Omit dose until resolved to ≤ grade 2, then ↓ 1 dose level
Febrile neutropenia (ANC < 1000/mm  (< 1.0 x 10  /L), fever > 38.3°C)	Omit dose, then: If resolved in ≤ 7 days, resume treatment at ↓ 1 dose level Mandatory: If resolved in > 7 days, discontinue patient from study drug treatment

Recommended dose modifications for INC280	
Worst toxicity CTCAE Grade a	During a cycle of therapy
Hemoglobin decreased (Anemia)	
Grade 1 (Hgb < LLN - 10.0 g/dL; < LLN - 6.2 mmol/L; < LLN - 100 g/L)	Maintain dose level
Grade 2 (Hgb < 10.0 - 8.0 g/dL; < 6.2 – 4.9 mmol/L; < 100 - 80 g/L)	Maintain dose level
Grade 3 (Hgb < 8.0 g/dL; < 4.9 mmol/L; < 80 g/L)	Omit dose until resolved to ≤ grade 2, then: If resolved in ≤ 7 days, resume treatment at the same dose level If resolved in > 7 days, then ↓ 1 dose level

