Grade 4	Omit dose until resolved to ≤ grade 2 and then ↓ 1 dose level Mandatory: If toxicity recurs, discontinue patient from study drug treatment.
RENAL	
Serum creatinine	
Grade 1 (> ULN - 1.5 x ULN)	Maintain dose level
Grade 2 (> 1.5 - 3.0 x ULN)	Omit dose until resolved to ≤ grade 1 or baseline, then resume treatment at the same dose level.
Grade 3 (> 3.0 - 6.0 x ULN)	Omit dose until resolved to ≤ grade 1 or baseline, then resume treatment at ↓ 1 dose level.
Grade 4 (> 6.0 x ULN)	Mandatory: Permanently discontinue patient from study drug treatment
HEPATIC	
Isolated Total Bilirubin elevation*	
Grade 1 (> ULN - 1.5 x ULN)	Maintain dose level
Grade 2 (> 1.5 - 3.0 x ULN)	Omit dose until resolved to ≤ grade 1, then If resolved in ≤ 7 days, maintain dose level If resolved in > 7 days, ↓ 1 dose level
Grade 3 (> 3.0 - 10.0 x ULN)	Omit dose until resolved to ≤ grade 1, then If resolved in ≤ 7 days, ↓ 1 dose level If resolved in > 7 days, discontinue INC280 permanently
Grade 4 (> 10.0 x ULN)	Mandatory: Permanently discontinue patient from study drug treatment
Isolated AST or ALT elevation	
Grade 1 (> ULN - 3 x ULN)	Maintain dose level
Grade 2 (> 3.0 - 5.0 x ULN)	Maintain dose level
Grade 3 (> 5.0 - 20.0 x ULN)	Omit dose until resolved to ≤ grade 1 (or ≤ grade 2 if grade 2 elevation at baseline) then

Recommended dose modifications for INC280	
Worst toxicity CTCAE Grade a	
During a cycle of therapy
 
If resolved in <math>\leq</math> 7 days, then resume treatment at the same dose level If resolved in <math>></math> 7 days, resume treatment at <math>\downarrow</math> 1 dose level

Grade 4 ( $> 20.0 \times$ ULN)	
For patients with clinical benefit from INC280 upon investigator's judgement:
 
 
Omit dose until resolved to <math>\leq</math> grade 1 (or <math>\leq</math> grade 2 if grade 2 elevation at baseline), then resume treatment at <math>\downarrow</math> 1 dose level. Only 1 dose reduction is allowed; if this AE reoccurs at Grade 3 or above, discontinue INC280 permanently.
 
 
For all other patients:
 
 
Mandatory: Permanently discontinue patient from study drug treatment
 

Combined elevations of AST or ALT and Total Bilirubinb,d	

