d If combined elevations of AST or ALT and total bilirubin do not meet the defined thresholds, please follow the instructions for isolated elevation of total bilirubin and isolated elevation of AST/ALT, and take a conservative action based on the degree of the elevations (e.g. discontinue treatment at the situation when omit dose is needed for one parameter and discontinue treatment is required for another parameter). After all elevations resolve to the defined thresholds that allow treatment re-initiation, restart the treatment either at the same dose or at one dose lower if meeting a criterion for dose reduction	
* Note: If total bilirubin > 3.0 x ULN is due to the indirect (non-conjugated) component only, and hemolysis as the etiology has been ruled out as per institutional guidelines (e.g., review of peripheral blood smear and haptoglobin determination), then ↓ 1 dose level and continue treatment at the discretion of the investigator.	
** Note: antidiarrheal medication is recommended at the first sign of abdominal cramping, loose stools or overt diarrhea	
*** During the whole duration of treatment with INC280, the patient is recommended to use precautionary measures against ultraviolet exposure (e.g., use of sunscreen, protective clothing and avoid sunbathing or using a solarium intensively).	

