**Table 6-4 Follow-up evaluations for selected toxicities\***

TOXICITY	FOLLOW-UP EVALUATION
HEMATOLOGICAL Febrile neutropenia, Neutropenia $\geq$ CTCAE grade 3 Thrombocytopenia $\geq$ CTCAE grade 3 Anemia $\geq$ CTCAE grade 3	Test weekly (or more frequently if clinically indicated) until $\leq$ CTCAE grade 2. Perform physical exam for check on bruising in case of major thrombocytopenia.
RENAL Serum creatinine $\geq$ CTCAE grade 2	Test weekly (or more frequently if clinically indicated) until $\leq$ CTCAE grade 1 or baseline. Patients will be instructed to increase hydration until resolution to $\leq$ CTCAE grade 1 or baseline.

TOXICITY	FOLLOW-UP EVALUATION
HEPATIC  Isolated total bilirubin elevation	
Total bilirubin CTCAE Grade 1: Monitor LFTs per protocol or more frequently if clinically indicated
 
Total bilirubin CTCAE Grade 2: Weekly monitoring of LFTs, or more frequently if clinically indicated, until resolved to <math>\leq 1.5 \times</math> ULN
 
Total bilirubin CTCAE Grade 3: Weekly monitoring of LFTs, or more frequently if clinically indicated, until resolved to <math>\leq 1.5 \times</math> ULN. If resolved in <math>> 7</math> days, after discontinuing the patient from INC280 permanently, the patient should be monitored weekly (including LFTs), or more frequently if clinically indicated, until total bilirubin have resolved to baseline or stabilization over 4 weeks
 
Total bilirubin CTCAE Grade 4: After discontinuing the patient from INC280 permanently, the patient should be monitored weekly (including LFTs), or more frequently if clinically indicated, until total bilirubin have resolved to baseline or stabilization over 4 weeks

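### Protocol Table 6-3 gives opposite instructions for isolated total bilirubin above 10.0 x ULN that is indirect only with hemolysis excluded: a mandatory permanent stop in the grade 4 row, reduced-dose continuation in footnote *

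*Protocol*

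**What the plan says.** Four places in the Protocol bear on this.

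- **Table 6-3, opening line (Section 6.3.2).** It sets the status of everything below it: "To be considered recommended dose modifications, unless otherwise specified as mandatory in this" table. Actions are recommendations by default and binding only where marked.
- **Table 6-3, grade 4 row.** In the block headed "Isolated Total Bilirubin elevation", total bilirubin above 10.0 x ULN carries the instruction "Mandatory: Permanently discontinue patient from study drug treatment". The row contains no exception and no pointer to a note.
- **Table 6-3, footnote *.** The asterisk sits on the block heading, not on one grade. Its trigger is a total bilirubin above 3.0 x ULN that "is due to the indirect (non-conjugated) component only, and hemolysis as the etiology has been ruled out as per institutional guidelines". Its action is a one-level dose reduction, with treatment continuing if the investigator so chooses.
- **Table 6-4, isolated bilirubin entries (Section 6.3.4).** The wording "after discontinuing the patient from INC280 permanently, the patient should be monitored weekly (including LFTs" (apart from the initial capital) opens the grade 4 entry without any condition. At grade 3 it applies only if resolution took more than 7 days. A note under the table says that it concerns monitoring only and sends the reader to Table 6-3 for dosing.

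**The concern.** A row marked mandatory is meant to leave the site no choice. A footnote on the same block gives the investigator a choice over a range that includes that row. Two sites with identical patients could act in opposite ways, each able to cite the table.

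The first stake is patient safety: hepatotoxicity is listed as an adverse event of special interest in Protocol Section 8.1.3.1 and SAP Section 2.8.2. The second is reporting. SAP Section 2.8.2 tabulates adverse events that lead to permanent discontinuation separately from those that require dose adjustment. The same event would be counted in one table or the other according to the line the site followed, and exposure would differ too.

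**Working it through.** No sample size, power or error rate is involved, so the check is whether the two triggers overlap and whether the two actions can both be followed.

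**Inputs (Table 6-3, total bilirubin in multiples of ULN)**

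| Line | Range | Further conditions | Action | Marked mandatory? |
|---|---|---|---|---|
| Grade 3 row | above 3.0, up to 10.0 | none | Hold until grade 1 or below; reduce one level if that takes 7 days or less, stop permanently if longer | No |
| Grade 4 row | above 10.0 | none | Stop permanently | Yes |
| Footnote * | above 3.0, no upper limit | Indirect component only; hemolysis excluded | Reduce one level; continuation at the investigator's choice | No |

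**Step 1: overlap with grade 4.** (3.0, ∞) ∩ (10.0, ∞) = (10.0, ∞). Every grade 4 value lies inside the footnote's range. A grade 4 patient who also meets the two further conditions satisfies both triggers.

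**Step 2: compatibility at grade 4.** Permanent discontinuation and continuation one level lower cannot both be carried out.

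**Step 3: is there a rule of precedence?**
- The opening line of Table 6-3 separates mandatory from recommended actions. It does not say whether a note can displace a mandatory row.
- Section 6.3.1 says that any grade 4 toxicity is first interrupted and then followed by reduction or discontinuation, and refers to Table 6-3. It returns the reader to the table in question.
- Table 6-4 presumes a permanent stop at grade 4 but disclaims any dosing role, so it cannot decide the matter. It does mean that a patient kept on drug under the footnote has no matching grade 4 follow-up entry.
- The grade 4 AST/ALT row of Table 6-3 writes its exception into the row: patients judged to benefit are handled separately, and only the rest are marked mandatory. The grade 4 bilirubin row does nothing similar.

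**Step 4: overlap with grade 3.** (3.0, ∞) ∩ (3.0, 10.0] = (3.0, 10.0]. The ranges overlap here as well, but the row is not marked mandatory. A conditional note that modifies a recommended action is an exception to it, not a contradiction.

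**Step 5: can the footnote be triggered in practice?** Yes. Table 7-4 has direct bilirubin measured once total bilirubin is grade 2 or higher, and Table 6-4 asks for fractionation above 2.0 x ULN. Sites will have the result that shows whether the elevation is indirect only.

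**The case against.** The strongest reply is that footnote * is a deliberate exception. It hangs on the block heading, so it attaches to every row, and a note with specific conditions is ordinarily read as a carve-out from general rows. That reading is available. It does not close the matter, because the opposite reading, that a mandatory label prevails over a discretionary note, is equally available and the text ranks neither.

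A second reply is that Section 6.3.1 requires planned departures from Table 6-3 to be approved by the sponsor's medical lead or designee, apart from urgent need, so sites would not diverge unchecked. This helps only once it is known that continuing is a departure. A site that reads the footnote as part of the table would see nothing to submit. Section 12 adds that no authorized deviations are permitted.

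A third reply is rarity, and it stands as a limit on size. Patients enter with total bilirubin at or below 1.5 x ULN (Section 5.2, criterion 7). Bilirubin is not among the related grade 3/4 events listed for this study in Section 1.2.1.2.1. Table 2-1 shows one grade 3 bilirubin dose-limiting toxicity and none at grade 4.

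Three stronger readings are tempting, and the documents do not support them:
- A reader might infer that grade 3 is equally contradictory. The grade 3 row is only recommended. The footnote is silent on a hold but does not waive one, and Section 6.3.1 has a general interruption rule for grade 3 treatment-related toxicities.
- A reader might infer that Table 6-4 presumes permanent discontinuation at both grades. At grade 3 it does so only when resolution takes more than 7 days.
- A reader might treat Table 6-4 as a competing dose rule. Its own note says that it is not.

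**Conclusion.** The inconsistency is real and narrow. It concerns isolated total bilirubin above 10.0 x ULN, due to the indirect component only, with hemolysis excluded. Both conditions are needed; an indirect elevation without the hemolysis work-up does not bring the footnote into play.

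For that patient, one line requires a permanent stop and the other permits continued dosing one level lower, with no stated order of precedence. Cases would be few and the documents give no incidence, so the effect on discontinuation counts and exposure cannot be quantified. No primary or key secondary result is shown to change. The point is worth acting on because the instructions are opposite, one of them is labelled a mandatory stop, and the correction is almost free.

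The conclusion assumes that the asterisk on the block heading applies to the whole block, as it is printed. If the sponsor meant it for grade 3 only, the conflict disappears, but the table does not say so. No view is taken on which clinical rule should govern.

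**What to change.** Reconcile footnote * with the grade 4 row of Table 6-3. State whether the note for indirect-only elevation with hemolysis excluded applies above 10.0 x ULN and, if so, how it ranks against the mandatory label. Then align the grade 4 isolated bilirubin entry in Table 6-4, so that its follow-up instruction fits whichever outcome the sponsor confirms. The same edit can say whether the grade 3 row's hold applies to patients handled under the footnote; that is a clarification, not a contradiction to resolve.

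The cost is a sentence of footnote wording and a matching line in Table 6-4, carried in an amendment. If dosing has ended by the time this is read, the useful step is a statement in the clinical study report on whether any such case occurred and how it was handled and counted.

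### Protocol Table 6-3: for purely indirect, non-hemolytic bilirubin above 10 x ULN, the note to the isolated-bilirubin block allows continued dosing while the grade 4 row requires a permanent stop, and the table does not say which prevails

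*Protocol*

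**What the plan says.** Protocol Table 6-3 has a block headed "Isolated Total Bilirubin elevation", and the heading carries an asterisk. Three parts of the table matter here.

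- **Grade 3 row (above 3.0 and up to 10.0 x ULN).** The dose is omitted until recovery to grade 1 or better. If that takes 7 days or less, dosing resumes one level down. For slower recovery the row reads "If resolved in > 7 days, discontinue INC280 permanently". It is not labelled mandatory.
- **Grade 4 row (above 10.0 x ULN).** "Mandatory: Permanently discontinue patient from study drug treatment". The row contains no exception.
- **Asterisk note, printed below the table.** "If total bilirubin > 3.0 x ULN is due to the indirect (non-conjugated) component only", and hemolysis has been excluded under institutional guidelines, the patient goes down one "dose level and continue treatment at the discretion of the investigator".

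The table's introduction treats its entries as recommendations except where they are marked mandatory. It does not mention the notes.

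Table 6-4 gives the follow-up evaluations. For slow-resolving grade 3 bilirubin, and in the same terms for grade 4, it describes what happens "after discontinuing the patient from INC280 permanently, the patient should be monitored weekly (including LFTs), or more frequently if clinically indicated". It has no branch for indirect bilirubin.

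**The concern.** One table appears to give two answers to the same question: whether a patient with a marked but purely indirect bilirubin rise stays on INC280. One answer is a compulsory permanent stop. The other is a lower dose at the investigator's discretion.

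Three things depend on the answer.

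- **Patient management.** Protocol Section 7.1.4 makes discontinuation obligatory for the laboratory abnormalities specified in Section 6. Which line governs decides whether that obligation applies. Hepatotoxicity is an adverse event of special interest (Protocol Section 8.1.3.1).
- **Who decides.** Section 6.3.1 requires sponsor medical approval for a planned variance from Table 6-3. The note asks only for investigator discretion.
- **Deviation reporting.** Section 12 allows no authorized deviations, and SAP Section 2.4 tabulates and lists all of them. The same conduct is compliant under the note and breaches a mandatory stop under the row.

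**Working it through.** No sample size, power or error rate is involved. The check compares ranges and instructions.

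**Step 1: where the note attaches.** The asterisk is on the block heading, not on a single grade row. The note therefore reaches every row in the block that its own trigger covers.

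**Step 2: the ranges.** Let B be total bilirubin in multiples of ULN.

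- Note: B > 3.0, no upper limit, and only if the rise is purely indirect and hemolysis is excluded.
- Grade 3: 3.0 < B ≤ 10.0.
- Grade 4: B > 10.0.

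The note and grade 3 overlap on 3.0 < B ≤ 10.0, which is all of grade 3. The note and grade 4 overlap on B > 10.0, which is all of grade 4. At B ≤ 3.0 the note is not triggered.

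**Step 3: the instructions for a patient who meets the note's conditions.**

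| B (x ULN) | Row | Note | Result |
|---|---|---|---|
| > 3.0 to 10.0 | Omit; then one level down, or permanent stop if recovery takes > 7 days; not labelled mandatory | One level down, continue at discretion | Note reads as an ordinary exception to a recommendation |
| > 10.0 | Permanent stop, labelled mandatory | One level down, continue at discretion | The two cannot both be followed |

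**Step 4: is there a rule of precedence?** The introduction to Table 6-3 ranks mandatory entries above recommended ones. It does not say whether a note is an exception to a mandatory row or yields to it. Section 6.3.1 tells sites to interrupt for any grade 4 toxicity until recovery to grade 1 and then to reduce or discontinue, but it refers back to Table 6-3 for the choice. It does not settle the matter.

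**Step 5: how the table writes exceptions elsewhere.** In the grade 4 row for isolated AST or ALT, patients judged to be benefiting may resume at a lower dose after recovery, and the mandatory stop is limited to all other patients. That exception sits inside the row. The grade 4 bilirubin row has nothing comparable.

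**Step 6: can the situation arise?** Protocol Table 7-4 has direct bilirubin measured once total bilirubin reaches grade 2, so a site will have the data to apply the note. Inclusion criterion 7 requires total bilirubin no higher than 1.5 x ULN at screening, so reaching the overlap means a rise from at most 1.5 to above 10.0 x ULN. The documents give no frequency.

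**The case against.** The strongest reply is that a note keyed to a block heading is normally an exception to the whole block. On that reading the note removes a narrow, worked-up subset, the grade 4 row governs everyone else, and nothing conflicts. The opposite reply also has textual support: the note is not marked mandatory, so it is only a recommendation and gives way to the row. Each reading is coherent, but they lead to opposite actions and no sentence chooses between them. The AST/ALT row weakens the first reading, because this table elsewhere writes an exception to a mandatory stop inside the row.

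Other parts of the defence stand and limit the point.

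- A reader might infer that the investigator may continue INC280 at any bilirubin above 3 x ULN. The note does not say that. The rise must be purely indirect, hemolysis must have been excluded, and the dose must come down one level.
- A reader might take the grade 3 rows to be in conflict as well. They are not marked mandatory, so there the note works as an ordinary exception.
- A reader might count Table 6-4 as a second contradiction. Its own footnote describes it as a monitoring schedule and refers to Table 6-3 for dose modifications. It is also silent about the note at grade 3, where the note causes no difficulty. Its silence at grade 4 is weak evidence.
- Safeguards exist: the general grade 4 interruption in Section 6.3.1, the limit of two dose-level modifications in Section 6.3.2, and the instruction in Section 7.1.4 to stop when continuing would harm the patient. None of them says which line governs.

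**Conclusion.** The point holds within a narrow range. For isolated total bilirubin above 10.0 x ULN that is purely indirect, with hemolysis excluded, Table 6-3 gives two incompatible instructions and no order of precedence. This rests on two readings of the text: the asterisk on the heading applies to the whole block, and the note's stated lower bound is its only bound.

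The practical size is small. The combination should be rare, though no rate can be given from the documents. No efficacy analysis is affected: the primary analysis uses the Full Analysis Set (SAP Section 2.7.2), and the deviations that remove a patient from the Per-Protocol Set (SAP Section 2.2) include none on dose modification. What remains is patient safety and consistent deviation reporting for an event of special interest.

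A reader might infer that the missing upper limit is itself a clinical error, or that the mandatory row must be the correct rule. The documents support neither inference. They show an overlap without a stated precedence, and the choice belongs to the sponsor's clinical team.

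**What to change.** The sponsor's clinical team should reconcile the asterisk note with the grade 4 row of the isolated total bilirubin block in Table 6-3. The revised text should state:

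1. which range of total bilirubin the note covers; and
2. whether the note applies to a row marked mandatory.

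Once that is settled, the grade 4 bilirubin follow-up text in Table 6-4 should be checked against the outcome, because it currently describes only patients who have been stopped.

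The cost is about one clause in a table note, plus that check. Protocol Section 12.1 requires protocol changes to be made by written amendment, so the clause would go into one. No change to the SAP, the sample size or any analysis is needed.
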